7.3 Data Analysis Plans

7.3.1 Evaluate acceptability of the intervention

To evaluate acceptability of the intervention, we will administer a satisfaction assessment to each participant after each follow-up study visit (T1 and T2) and conduct post-intervention interviews at T2. We will report the acceptability rate at T1, along with an exact 95% confidence interval.

7.3.2 Analysis of interview data

In the follow-up interviews, we will seek input from participants in the treatment arm on: (1) the relevance of intervention components; (2) intervention acceptability and tolerability; (3) language (tone and phrasing, tailoring); and (4) emotional and cultural sensitivity. Participants assigned to the waitlist control arm will be asked to discuss: (1) the relevance of the study's subject matter; (2) their experiences regarding cancer-related communication with their children; (3) their expectations of the study intervention, which will be made available at the end of their participation, and (4) perceptions of, and feedback on, study design and operations.

We will use content analysis, a widely accepted qualitative analysis approach in health research, to identify major themes from interviews.²⁰ The study team will review interview transcripts, coding and categorizing the data by expanding and collapsing categories until thematic saturation is reached.²¹ We will use best practices for qualitative research such as member checking, and creation of an audit trail.²² We will use this

feedback to refine the intervention prior to launching the full efficacy trial. We will use qualitative analysis software to aid with analyses. Descriptive statistics from the quantitative rating scale and qualitative interview data will be collected concurrently, analyzed separately, and the two sets of findings converged.²³

7.3.3 Evaluate feasibility of the intervention

To evaluate feasibility of intervention, we will report the percentage of patients who are approached about the study who:

- Enroll in the intervention (percent approached)
- Complete the intervention at each time point (percent completed per visit and overall)

We will also use descriptive statistics to assess the demographic characteristics of patients who enter, remain in, and drop out of the study. Comparisons will be made using Wilcoxon Rank sum tests for continuous characteristics and Fisher's Exact tests for categorical characteristics.

In addition, we will evaluate feasibility of study procedures including:

- Number of patients screened each month
- Number of contacts necessary to enroll participants and schedule follow-up appointments
- Proportion of completed study measures at each visit

Although adverse events are unlikely, we will examine the procedures for adverse event reporting and the study teams' response should this occur.

We will use qualitative analyses of the semi-structured interview data to explore barriers and facilitators to participation, including reasons for enrollment, non-participation (e.g. fears of unintended outcomes, competing demands, etc.), ineligibility, or withdrawal and use this information to refine study procedures in preparation for a larger-scale study.

7.3.4 Explore impact of intervention on target outcomes

We will report on changes in CSES scores from pre- (T0) to post-intervention (T1, T2) . This pilot study is not designed nor powered to detect differences as the primary objectives are to evaluate the acceptability and feasibility of the intervention as compared to treatment as usual.

We will also report on changes in other patient-reported outcomes of interest including GAD-7 and PHQ-2 scores.

We will use descriptive statistics to report on the percentage of patients who engage in any communication behaviors about cancer with their children, the depth of their discussion, and their assessments of how their children responded to these conversations.

Data from this study will be used for preliminary estimates (for which the CSES will be the primary outcome measure) to power a future R01 testing the intervention. The projected effect size will be based on mean differences in SD for the CSES from this pilot study.

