1.0 BACKGROUND AND RATIONALE

1.1 Study Synopsis

This is a single center, two-arm pilot randomized controlled trial (RCT) evaluating the feasibility and acceptability of a novel psychosocial intervention, Families Addressing Cancer Together (FACT) delivered as a mobile response web application (mobile web app). FACT is a theory-guided, psychoeducational intervention designed to improve parents' confidence and ability to talk about their cancer with their minor children. We will enroll 40 patients with cancer who have a minor child to participate in this 6-week study. The primary hypothesis being tested is that an intervention that assists parents with their communication needs with their children can be feasible, acceptable, and improve parental communication self-efficacy when compared with a waitlist control condition. Findings from this study will inform a future grant application to further test this intervention in a randomized full efficacy trial.

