1.3 Purpose and Rationale

This pilot study will provide the necessary data to inform the development and full efficacy testing of a novel psychosocial intervention to support parents with cancer in communicating with their children about cancer. The research questions to be answered by this study are whether the intervention being tested can be feasible, be acceptable, and provide preliminary estimates of improvement in parental communication and psychological outcomes as compared to a waitlist control condition.

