2.3 Exploratory Objectives

3.0 PATIENT ELIGIBILITY

3.1 Inclusion Criteria

Confirmation of eligibility criteria is required for all potential study participants prior to study enrollment. Participants will be eligible for study participation as defined by the inclusion and exclusion criteria as follows:

- 3.1.1. Informed consent reviewed and signed;
- 3.1.2. Age equal to or above 18 years;
- 3.1.3. Ability to understand and comply with study procedures;
- 3.1.4. Able to complete all study measures and visits in English;
- 3.1.5. Be a parent (defined as biological, adoptive, foster, or step-parent), kin caregiver (defined as a relative or someone with a significant emotional relationship who provides full-time care and nurturing of a child), or legal guardian of a child age 3 to 17 years of age who can speak and understand English;
- 3.1.6. Have a diagnosis of Stage II-IV (or equivalent) invasive solid tumor not in surveillance or survivorship

[figure not shown]

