4.3.5 Self-report measures

Participants will complete several outcome measures. Participants may complete some or all of the surveys and can skip any questions they find distressing.

The measuring instruments, schedule of administration, and estimated duration are listed in Table 1.

Table 1. Measuring instruments

Domain	Measure	Time (min)	Arm	Schedule
Demographic form	Demographic form	2	Both	T0
Performance status	Eastern Cooperative Oncology Group Performance Status Scale (ECOG)	1	Both	T0
Illness beliefs	Two items, Investigator-designed, minimally adapted for this study	1	Both	T0
Parental cancer communication beliefs & behaviors	Parental Cancer Communication Questionnaire (PCCQ)	5	Both	T0, T1, T2
Anxiety symptoms	Generalized Anxiety Disorder – 7 (GAD-7)	3	Both	T0, T1, T2
Depression symptoms	Patient Health Questionnaire-2 (PHQ-2)	1	Both	T0, T1, T2
Communication self-efficacy	Communication Self-Efficacy Scale (CES-E)	3	Both	T0, T1, T2
Parent-child relationship	Single-item assessment, adapted from Sandler, et al.	1	Both	T0, T1, T2
Acceptability	FACT Satisfaction scale	3	Treatment	T1, T2
Other resource use	Investigator-designed, single item	1	Both	T0, T2

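### Section 7.3.4 describes CSES as change from T0, names no T0 or stratum adjustment and no interval, yet carries the pilot effect size to the R01

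*Combined protocol and SAP*

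**What the plan says.** All references are to the combined protocol and SAP.

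- Section 7.3.4 describes the CSES analysis in one sentence: "We will report on changes in CSES scores from pre- (T0) to post-intervention (T1, T2". It names no model, covariate, between-arm estimator or interval.
- The same section adds a disclaimer: "This pilot study is not designed nor powered to detect differences".
- It then makes CSES the primary outcome measure for powering a future R01 and closes with: "The projected effect size will be based on mean differences in SD for the CSES from this pilot study". It does not say which time point is meant or which SD is the divisor.
- The comparison with waitlist is stated elsewhere. The hypothesis in section 1.1 is that the intervention can "improve parental communication self-efficacy when compared with a waitlist control condition". Section 1.3 asks whether it can "provide preliminary estimates of improvement in parental communication and psychological outcomes as compared to a waitlist control condition".
- The only interval in the plan is for acceptability. Section 7.3.1 says: "We will report the acceptability rate at T1, along with an exact 95% confidence interval". Section 7.2 gives its expected width.
- Table 1 in section 4.3.5 schedules the scale (abbreviated CES-E there) in both arms at T0, T1 and T2. Section 4.3.2.1 requires T0 before randomization, and section 4.3.2.2 stratifies 1:1 allocation by advanced or non-advanced disease.

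Section 2.3, on exploratory objectives, is a heading without text in the copy reviewed. That may be an extraction gap, and nothing here rests on it.

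**The concern.** The CSES estimate is an output the pilot is meant to produce: sections 1.1 and 1.3 say the study informs a full efficacy trial, and 7.3.4 assigns CSES that role. Two features weaken it.

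First, a summary of change from T0, compared between arms, uses the T0 score inefficiently. In a randomized trial, a comparison that takes T0 CSES as a covariate is at least as precise for any correlation, and strictly more precise when the correlation is below 1.

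Second, an effect size from 20 to 27 people per arm is very uncertain. The plan attaches an exact interval to the acceptability rate but none to the CSES effect size that goes forward. A reader of the later grant application would see a number without its uncertainty. With T1 or T2 and the divisor left open, that number could also be chosen after the data are seen.

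**Working it through.** **1. The plan's own precision figure.** Section 7.2 gives a 95% exact binomial CI of 50.9% to 91.3% for a 75% rate at n=20, with precision no worse than +/-23%. The Clopper-Pearson interval for 15/20 is 50.9% to 91.3%, and the largest half-width over all outcomes at n=20 is 22.8%. Both reproduce. The plan gives no CSES SD, effect size or interval to reproduce.

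**2. Inputs for CSES.**
- Per-arm numbers: sections 1.1 and 4.1 give 40 patients, so 40/2 = 20 per arm. Section 7.2 gives 55, so 55/2 = 27.5, taken as 27. Both assume no loss to follow-up.
- Effect size d and T0-to-follow-up correlation r are not in the documents. They are assumed, with r shown over a range.

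**3. Change score against T0 adjustment.** Assume equal SDs at T0 and follow-up, set to 1. The per-person variance is 2(1-r) for a change score and 1-r² with T0 as covariate. The ratio is (1-r²)/[2(1-r)] = (1+r)/2. The standard error (SE) of the arm difference is the square root of (2/n × variance), here with n=20 per arm.

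| r | Variance ratio | SE, change score | SE, T0-adjusted | Fall in SE |
|---|---|---|---|---|
| 0.3 | 0.65 | 0.374 | 0.302 | 19% |
| 0.5 | 0.75 | 0.316 | 0.274 | 13% |
| 0.7 | 0.85 | 0.245 | 0.226 | 8% |
| 0.8 | 0.90 | 0.200 | 0.190 | 5% |

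These are large-sample ratios. A simulation at 20 per arm (20,000 runs per value of r; model with arm, T0 and stratum) gave 95% CIs narrower by 18%, 12%, 6% and 4%, so the small-sample cost of the extra terms does not cancel the gain.

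**4. Uncertainty of the effect size.** The 95% CI for a standardized mean difference comes from inverting the noncentral t distribution with 2n-2 degrees of freedom. It applies when the divisor is the SD of the scores compared. For an observed d of 0.5:
- 20 per arm: -0.13 to 1.13.
- 27 per arm: -0.04 to 1.04.

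For a two-sided 5% t-test at 80% power, d=0.5 needs 64 per arm. The upper limits need 14 and 16 per arm. The lower limits are below zero, so no sample size is defined there.

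T0 adjustment narrows this uncertainty but does not remove it. At r=0.5 and 20 per arm, the simulated mean CI width falls from 1.27 to 1.12 SD, still more than half an SD either side.

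**5. Why the divisor must be named.** A difference of 0.5 on the raw-score SD becomes 0.5/√[2(1-r)] on the change-score SD: 0.5/√1.4 = 0.42 at r=0.3, and 0.5/√0.4 = 0.79 at r=0.8. The same data can be reported as quite different effect sizes.

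**The case against.** The strongest defence is that this is an exploratory outcome in a pilot that disclaims power, and that 7.3.4 is brief rather than wrong. Much of that stands. The disclaimer makes it reasonable to have no hypothesis test, and acceptability as primary objective explains why it has the planned interval. The disclaimer does not explain why an effect size meant for the R01 goes forward without one.

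Four stronger readings are tempting, and the documents do not support them.

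- **That the plan deliberately chose an inferior analysis, or no comparison with waitlist.** Section 7.3.4 does not restrict itself to change scores and names no estimator. A T0-adjusted model also describes change. Sections 1.1 and 1.3 make the comparison the evident intent. The precision figures apply to the text read as written.
- **That the R01 will be underpowered.** If the point estimate alone sized the R01 at 80% power, 32% to 35% of pilots at a true d of 0.3, or 22% to 25% at 0.5 (both assumed; 27 and 20 per arm), would lead to true power under 50%. But the plan says only that the projection will be based on the pilot, and sizing is left to a later application. T0 adjustment hardly changes these shares: at 20 per arm and r=0.5, from 34.6% to 32.1% and from 25.2% to 23.1%.
- **That the SD will be mismatched.** Sizing on a change-score SD and then analysing unadjusted follow-up scores would give 59% power at r=0.7 or 44% at r=0.8. No section proposes that pairing; with a change-score analysis, power is 80% to 81%.
- **That omitting the stratum is costly.** The gain is small and cannot be quantified from the documents. The term belongs in the model because allocation is stratified on it.

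**Conclusion.** The point holds as a free improvement to an exploratory analysis. Section 7.3.4 names no T0 or stratum adjustment and no CSES interval, and it leaves the time point and divisor of the R01 effect size open. That these are absent is plain from the text. The size of the precision loss is conditional: 19% to 5% of the SE for r from 0.3 to 0.8, assuming equal SDs at T0 and follow-up and a change score compared between arms. The need for an interval does not depend on r; at either enrolment figure, the CI around an observed d of 0.5 runs from just below zero to above 1. The R01 power and SD-mismatch figures illustrate what could follow from later sizing decisions and are not consequences of this plan. The primary acceptability analysis and the 75% rule are unaffected.

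**What to change.** In section 7.3.4:

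1. Estimate the FACT-minus-waitlist CSES difference at T1 and T2 from a linear (mixed) model with arm, T0 CSES and disease-status stratum, and report each difference with a 95% CI.
2. State in advance whether T1 or T2 supplies the R01 effect size.
3. Amend the last sentence so that this effect size goes forward only with its CI, the CSES SD used as divisor, and the T0-to-follow-up correlation.

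The cost is two or three sentences and a few lines of code. CSES is already collected in both arms at all three times, and the stratum is known at randomization. No new data, visits or participants are needed.

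Optional, for the grant application: size the R01 on a CSES difference judged worthwhile in advance, using the pilot mainly for the SD and correlation. This addresses the noise in the point estimate more directly than adjustment does, but the change to 7.3.4 need not wait for it.

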7.4 Data Management/Audit

The PI and study coordinator will coordinate and manage data for quality control assurance and integrity. The recorded interview data will be kept in a password-protected electronic file housed within a secure server within the UNC Department of Psychiatry of the UNC School of Medicine. Interview data will be immediately erased from external audio recorders after confirming successful transfer to the secure server. De-identified transcriptions will be entered into a qualitative analysis program which is accessed on password-protected, encrypted computers by the study team.

Several elements will be embedded within the REDCap database in order to ensure data quality and compliance. These include a “Data History” function which generates and records an audit trail for all data; therefore, all data will be recorded with a full history including values entered. Any changes to data will be recorded and specify when the change occurred, which REDCap user changed the value, and the time of the change.

As an investigator-initiated study, this trial will also be audited by the Lineberger Cancer Center audit committee every six or twelve months, depending on the participation of affiliate sites.

8.0 STUDY MANAGEMENT

8.1 Institutional Review Board (IRB) Approval and Consent

It is expected that the IRB will have the proper representation and function in accordance with federally mandated regulations. The IRB will approve the consent form and protocol.

In obtaining and documenting informed consent, the investigator will comply with the applicable regulatory requirement(s) and should adhere to Good Clinical Practice (GCP) and to ethical principles that have their origin in the Declaration of Helsinki.

Before recruitment and enrollment onto this study, the patient will be given a full explanation of the study and will be given the opportunity to review the consent form. Each consent form must include all the relevant elements currently required by federal, local, or state regulations. Once this essential information has been provided to the patient and the investigator is assured that the patient understands the implications of participating in the study, the patient will be asked to give consent to participate in the study by signing an IRB-approved consent form.

Prior to a patient's participation in the trial, the written informed consent form will be signed and personally dated by the patient and by the person who conducted the informed consent discussion. The participant will receive copies of the signed consent form(s).

8.2 Required Documentation

Fulfillment of the following documentation must precede initiation of any study procedures:

- Delegation of Responsibilities Log and study personnel training records
- Official IRB approval letter for the protocol and informed consent
- Signed CV (within 2 years) and medical or professional licensure for all study investigators; supplemental documentation, if applicable, to document investigation qualifications may be added
- Copy of the approved protocol and associated documents, including
 - Informed consent documents
 - Recruitment materials
 - Other written material to be given to study participants
- IRB roster(s) and correspondence

8.3 Registration Procedures

Once patients have consented to participate in this trial, they will be assigned a unique and random study ID to be used throughout the study. A sole file linking the study ID to the participant's identifiers will be stored on a password protected file on a secure server maintained by the School of Medicine. Physical consent forms will be kept within a locked file cabinet and office.

All participants will also be registered in Oncore™.

8.4 Adherence to the Protocol

Except for an emergency situation in which proper care for the protection, safety, and well-being of the study patient requires alternative treatment, the study shall be conducted exactly as described in the approved protocol.

8.4.1 Emergency Modifications

UNC investigators may implement a deviation from, or a change of, the protocol to eliminate an immediate hazard(s) to trial participants without prior UNC IRB approval.

For any such emergency modification implemented, a UNC IRB modification form must be completed by UNC Research Personnel within five (5) business days of making the change.

8.4.2 Single Patient/Participant Exceptions

Any request to enroll a single participant who does not meet all the eligibility criteria of this study requires the approval of the UNC Principal Investigator and the UNC IRB.

8.4.3 Other Protocol Deviations/Violations

According to UNC's IRB, a protocol deviation is any unplanned variance from an IRB approved protocol that:

- Is generally noted or recognized after it occurs
- Has no substantive effect on the risks to research participants
- Has no substantive effect on the scientific integrity of the research plan or the value of the data collected
- Did not result from willful or knowing misconduct on the part of the investigator(s).

An unplanned protocol variance is considered a violation if the variance meets any of the following criteria:

- Has harmed or increased the risk of harm to one or more research participants.
- Has damaged the scientific integrity of the data collected for the study.
- Results from willful or knowing misconduct on the part of the investigator(s).
- Demonstrates serious or continuing noncompliance with federal regulations, State laws, or University policies.

If a deviation or violation occurs, study personnel will follow the guidelines below:

Protocol Deviations: UNC personnel will record the deviation in OnCore® (or other appropriate database set up for the study), and report to any sponsor or data and safety monitoring committee in accordance with their policies. Deviations should be summarized and reported to the IRB at the time of continuing review.

Protocol Violations: Violations should be reported by UNC personnel within one (1) week of the investigator becoming aware of the event using the same IRB online mechanism used to report UPIRSO.

Unanticipated Problems Involving Risks to Participants or Others (UPIRSO): Any events that meet the criteria for "Unanticipated Problems" as defined by UNC's IRB (see section 6.1) must be reported by the Study Coordinator using the IRB's web-based reporting system.

8.5 Amendments to the Protocol

Should amendments to the protocol be required, the amendments will be originated and documented by the Principal Investigator at UNC. It should also be noted that when an amendment to the protocol substantially alters the study design, potential risk to participants, or other elements a revised consent form might be required.

The written amendment, and if required the amended consent form, must be sent to UNC's IRB for approval prior to implementation. Amendments with modifications to the study design must be approved by UNC Protocol Review Committee prior to IRB submission.

8.6 Record Retention

Study documentation includes all Case Report Forms, data correction forms or queries, source documents, Sponsor-Investigator correspondence, monitoring logs/letters, and regulatory documents (e.g., protocol and amendments, IRB correspondence and approval, signed patient consent forms).

Source documents include all recordings of observations or notations of clinical activities and all reports and records necessary for the evaluation and reconstruction of the clinical research study.

Government agency regulations and directives require that all study documentation pertaining to the conduct of a clinical trial must be retained by the study investigator. In accordance with these parameters, documents should be kept on file until three years after the completion and final study report of this investigational study, with exception of interview audio files which will be deleted upon study closure.

